### 3.2 Allocation to Treatment Groups and Blinding

The overall design will randomize participating schools to the school intervention (S+) or usual care (S-) based on predefined strata (defined by size, location, public school or public charter school status, etc.) to enhance balance. When children with uncontrolled asthma and their caregivers present in the primary care offices and provide consent to participate, these patients will be randomized either to a primary care CHW (child-level intervention) (P+) or usual care (P-), and this randomization will be stratified by the child's current elementary school and clinic of recruitment to ensure balanced assignment in the factorial design.

### 3.3 Study Duration, Enrollment and Number of Sites

### 3.3.1 Duration of Study Participation

The study duration per subject will be up to 24 months, if participant has not completed the assigned study interventions within the first 12 months of participation.

## 3.3.2 Total Number of Study Sites/Total Number of Subjects Projected

The study will be conducted at approximately six healthcare sites, including CHOP primary care sites (Cobbs Creek, Karabots and South Philadelphia), CHOP ED and approximately two Federally Qualified Health Centers serving West Philadelphia, and no greater than 40 elementary schools according to the number of schools agreeing to participate. This includes as many as 30 public schools and as many as ten public charter schools located in the West Philadelphia area.

Recruitment will stop when 640 subjects are enrolled. It is expected that at least 600 children will be evaluable subjects.

# 3.4 Study Population.

### 3.4.1 Inclusion Criteria

- 1) Parents (guardians) and their children ages 5-13 years
  - Children will include those who:
    - a) Have a diagnosis of asthma
    - b) Have uncontrolled Asthma (as evidenced by one or more asthma exacerbations requiring oral steroids within the past year -OR- 2 ED visits for

- asthma within the past year -OR- 1 inpatient admission for asthma within the past year).
- c) Reside in one of seven West Philadelphia zip codes:(19104, 19131, 19139, 19142, 19143, 19151, 19153)
- d) Are enrolled in elementary school
- e) Are patients at primary care provider practices at CHOP CN Cobbs Creek, CHOP CN Karabots, CHOP CN South Philadelphia, PAMCOP or a Federally Qualified Health Center serving West Philadelphia residents.
- 2) Parental/guardian permission (informed consent) and if appropriate, child assent.
- 3) English Speaker

### 3.4.2 Exclusion Criteria

- 1) Subjects with other chronic respiratory illnesses such as cystic fibrosis
- 2) Cyanotic congenital heart disease
- 3) MRCP-Mental retardation and/or cerebral palsy
- 4) Severe Neurological Disorder
- 5) Cyanotic congenital heart disease
- 6) Parents/guardians or subjects who, in the opinion of the Investigator, may be non-compliant with study schedules or procedures.
- 7) Those who do not live in West Philadelphia (zip codes: 19104, 19131, 19139, 19142, 19143, 19151, 19153)

Subjects that do not meet all of the enrollment criteria may not be enrolled. Any violations of these criteria must be reported in accordance with IRB Policies and Procedures.

#### 4 STUDY PROCEDURES

### 4.1 Screening Visit

- Medical Record Review of the child
- Verbal consent/complete eligibility screening
- Identify child's elementary school
- Schedule first visit

### 4.2 Study Treatment Phase

### 4.2.1 Study Visit 1 (Enrollment)

All study participants will complete the following:

- Consent/Assent
- Baseline Questionnaire
- Clinical and vital sign measurements of child [weight, height, BMI, blood pressure, pulse, temperature, pulse oximetry (SpO2)]
- Pulmonary function test (spirometry) with child if not obtained from medical record
- 2-week parental recall of symptoms, school absences, and work days missed
- Asthma Control Questionnaire
- Child Asthma Risk Assessment Tool (CARAT)
- Caregiver's Quality of Life Questionnaire
- Caregiver Needs Assessment
- Cost Analysis Parent Questionnaire
- Observe MDI technique and complete MDI Checklist
- Assess possible adverse events from date of enrollment

# 4.2.2 Study Visits 2, 3, and 4 (Primary Care Office Visits)

Primary Care office visits will be scheduled for 3, 6 and 9 months post study enrollment. All study participants will complete the following:

- Asthma Control Questionnaire
- Clinical and vital sign measurements of child [weight, height, BMI, blood pressure, pulse, temperature, pulse oximetry (SpO2)]
- Pulmonary function test (spirometry) with child if not obtained from medical record.
- 2-week parental recall of symptoms, school absences, and work days missed
- Cost Analysis Parent Questionnaire
- Assess possible adverse events
- Review child's medical record for utilization of healthcare services
- Review care coordination goals and direct to community resources

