Child Asthma Risk Assessment Tool (CARAT) modified		X								X	
Initial Home Environmental Assessment			X								
Asthma Knowledge Quiz			X		X				X	X	
Caregiver Needs Assessment		X									
Community Health Worker Goal Tracking		X	X	X	X	X	X	X	X	X	
Asthma Management Education			X	X	X	X	X	X	X		
Follow-Up Questionnaire with Asthma Symptom Recall						X	X	X		X	X
Follow-Up Home Environmental Assessment				X	X				X		
School Nurse Checklist		X								X	
Initial Classroom Environmental Assessment		X									
Follow-Up Classroom Environmental Assessment						X					
School Based Asthma Therapy Intake Survey		X									
CHW Caregiver Satisfaction Survey											X

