This will be a randomized controlled clinical trial of children diagnosed with asthma, ages 5-13 years old randomized after consenting to primary care CHW (P+) or no primary care CHW (P). In the Primary Care Based CHW arm (P+) the CHW will provide one-on-one asthma education in the office and home, environmental trigger mitigation in the home, assistance in identifying care coordination goals with linkages to resources to address barriers and will facilitate communication between the health care provider and the family. The intervention group (P+) will have a total of four visits to the primary care office where they will receive asthma self-management education in the office, review of medications, asthma control assessment, pulmonary function assessment and care coordination. They will receive three intervention home visits where the CHW will reinforce asthma selfmanagement skills, assess the home environment for asthma triggers, provide supplies for environmental remediation and educate caregiver regarding asthma trigger avoidance techniques. This arm will also be eligible for school based direct observed asthma treatment called school-based asthma therapy (SBAT). At twelve months the intervention group will receive an end of study assessment in the primary care office and in the home. The control group will not receive any of the aforementioned services for one year after enrollment. They will be referred to community asthma classes administered by CAPP. After one year the control group will receive one home visit at which time they will receive an environmental home assessment and environmental remediation supplies.

Children in both arms (P+ and P-) may attend an intervention school. Roughly 30 elementary schools have been identified by the School District of Philadelphia to participate in this project. Several public charter schools including three public charter schools served by school-based health centers managed by Education Plus Health have been identified to participate in this study. One half of the schools (S+) will be randomized to receive **Open Airways for Schools** *Plus* designed by Clark, et. al., an EBI asthma education and care coordination model for schools, and School Based Asthma Therapy (directly observed controller medication use).  The remaining half of the identified schools (S-) will be offered training on how to implement the two evidence-based programs in years 4 and 5 of the project.

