Families of children who are not randomized to the primary care intervention will be offered Community Asthma Prevention Program (CAPP) asthma classes, conducted at community sites, which are available to the general public. Data will be collected from the control arm at 3, 6, 9 months by phone or in person. At 12 months an office visit will be scheduled, pulmonary function testing (spirometry) performed and end-of-study data collected. After completing the study these patients will receive one home visit from a primary care CHW to complete an asthma trigger assessment and distribute asthma trigger reduction supplies.

Schools who are not randomized to intervention arm will be offered training after the study data collection period has ended and during the last year of grant funding in how to implement the school asthma interventions and will be provided with information on how to sustain these interventions by obtaining reimbursement from health insurance companies for school CHW services.

During the COVID-19 pandemic, the study activities detailed above will be modified as follows to preserve the health and safety of participants, healthcare professionals, study staff and the West Philadelphia community. Data collection for study visits may take place remotely by telephone or video conference using a HIPAA-compliant application licensed by CHOP. In person clinic visits solely for study purposes will take place as permitted by CHOP Research Institute Policy and Guidelines. Study activities designed to take place in a school setting may take place remotely by telephone or video conference using a HIPPA-compliant application licensed by CHOP.

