# 4.3 Primary Care Based Intervention:

### 4.3.1 Study Visit 1 (Baseline)

Additional components of Visit 1 will include:

- Care coordination goals developed with the parent/caregiver
- Coordinate school forms, medications and devices

#### **4.3.2** Home Visit 1

Initial home visit scheduled within 2 weeks of enrollment. Primary care CHW will do the following with the child and parent/caregiver:

- Administer home environmental assessment survey
- Take photographs of child's bedroom and home's main living area (environmental remediation assessment)
- Educate about asthma basics and asthma trigger avoidance
- Review asthma medications and asthma care plan
- Administer Asthma Knowledge Quiz
- Observe MDI technique with either the child or the parent/caregiver
- Give asthma supplies tailored to environment and show caregiver how to use

- Assess possible adverse events
- Review child's medical record for utilization of healthcare services
- Establish care coordination goals and refer to community resources as needed

#### **4.3.3** Home Visit 2

Second home visit is scheduled within 4 weeks of enrollment. Primary care CHW will do the following with the child and caregiver/parent:

- Complete follow-up home environmental assessment
- Educate about types of asthma medications, how they work and how to use them properly
- Review asthma medications and asthma care plan
- Give asthma supplies tailored to environment and show caregiver how to use
- Observe MDI technique with the child or the parent/caregiver
- Assess possible adverse events
- Review child's medical record for utilization of healthcare services
- Review care coordination goals and refer to community resources as needed

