## 4.3.5 Study Visits 2, 3, and 4 (Primary Care Office Visits)

Additional components of Study Visits 2, 3, and 4 will include:

- Coordinate school forms, medications and devices
- Teach asthma care plan
- Review care coordination goals and refer to community resources as needed

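### Protocol 4.2.2 gives all participants, controls included, care-coordination goal review and direction to community resources at 3, 6 and 9 months, a P+ service that section 3.1 withholds from controls for a year

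*Protocol*

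**What the plan says.** Protocol 4.2.2 covers Study Visits 2, 3 and 4, at 3, 6 and 9 months. Its list is for all study participants, and the final item is "Review care coordination goals and direct to community resources".

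Other parts of the protocol describe the control condition differently:

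- **Section 3.1** includes in the P+ service "assistance in identifying care coordination goals with linkages to resources to address barriers". It then states: "The control group will not receive any of the aforementioned services for one year after enrollment". The one referral it names for controls in that year is: "They will be referred to community asthma classes administered by CAPP".
- **Section 3.1.3** describes control contact at these months as data collection: "Data will be collected from the control arm at 3, 6, 9 months by phone or in person".
- **Section 4.3.1**, within the primary care intervention, is where goals are first set, as an additional component of Visit 1: "Care coordination goals developed with the parent/caregiver".
- **Section 4.3.5** gives, as an additional P+ component of Visits 2 to 4: "Review care coordination goals and refer to community resources as needed".

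Table 1 of the Protocol has a row "Community Health Worker Goal Tracking" marked at these visits, but the table does not separate the arms.

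**The concern.** One activity is listed both as common to all children and as extra for P+ at the same three visits, and section 3.1 forbids it for controls. All three visits fall between Study Visit 1 and Study Visit 5, the interval over which Protocol 6.3.2 measures the primary endpoint.

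If staff work from 4.2.2, control families could be directed three times to resources beyond the planned CAPP classes. Controls would then receive part of the treatment under test, which would be expected to narrow P+ v P-. Connection to resources is also a hypothesised mediator in SAP Table 6.2.3, so the difference between arms on that mediator could shrink too. The mediator point is secondary, because SAP 9.2 already expects mediation analyses to fail for lack of numbers.

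There is also a reporting problem that does not depend on any loss of power. The CONSORT checklist appended to the SAP asks for each group's intervention in enough detail to replicate it. From this text a reader cannot tell what usual-care families received.

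**Working it through.** **Comparison of the text**

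| Protocol section | Who it covers | Goals and resources at 3, 6 and 9 months |
|---|---|---|
| 3.1 | Controls | Withheld for one year; CAPP class referral only |
| 3.1.3 | Controls | Data collection; CAPP classes offered |
| 4.2.2 | All participants | Goal review and direction to resources |
| 4.3.5 | P+ | Goal review and referral, as an additional component |

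1. Sections 4.2.2 and 3.1 cannot both be followed for a control child.
2. Sections 4.2.2 and 4.3.5 are also inconsistent. An item already common to everyone is not additional for P+.
3. The all-participant lists for Visit 1 (4.2.1) and Visit 5 (4.2.3) do not contain the item, and goals are set only under 4.3. Controls therefore have no goals to review, which points to a carry-over from the P+ list.
4. What remains for controls is the direction to community resources, with no limit to CAPP classes.
5. The instruction could be carried out. Protocol 9.7.1 allows a research assistant or a primary care CHW to collect data from any individually randomized participant, so the person contacting a control family may be someone whose job includes linking families to resources.

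**Illustration of dilution**

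The documents give no estimate of how much controls would gain. Let *f* be the assumed share of the P+ effect that they gain.

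Inputs, from the revised power table in SAP section 8:

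- P+ main effect of 0.35 SD with zero interaction
- n=432 or n=600
- stated power for this contrast of 0.95 and 0.99 respectively

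Formula, for two equal arms with outcome SD 1 and two-sided 5% significance, treating this within-school contrast as unaffected by clustering:

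Power = Φ(0.35 × (1 − f) / SE − 1.96), with SE = 2/√n.

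SE is 2/√432 = 0.0962 and 2/√600 = 0.0816.

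At f = 0 this gives Φ(0.35/0.0962 − 1.96) = 0.953 and Φ(0.35/0.0816 − 1.96) = 0.990. Both match the SAP's simulated values, so the approximation is adequate here.

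| f | n=432 | n=600 |
|---|---|---|
| 0 | 0.953 | 0.990 |
| 5% | 0.933 | 0.983 |
| 10% | 0.906 | 0.971 |
| 20% | 0.829 | 0.929 |

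The largest f that keeps a given power is f = 1 − (1.96 + z) × SE / 0.35:

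| Power kept | z | n=432 | n=600 |
|---|---|---|---|
| 0.90 | 1.282 | 0.109 | 0.244 |
| 0.80 | 0.842 | 0.230 | 0.346 |

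The n=432 column is the pessimistic end. It counts only children in cells a to d, whereas SAP section 2 also uses cells e and f for the child-level contrast. The number in e and f is not given. Protocol 3.3.2 expects at least 600 evaluable children in total.

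**The case against.** The strongest reply is that the protocol, read as a whole, already settles what controls receive. Section 3.1 is categorical. Section 3.1.2 assigns a primary care CHW only to children randomized to that arm. Section 5.1 limits use of the needs assessment for tailoring education to P+. Goals exist only in P+. Section 4.2.2 is also hard to use as a literal script for controls: it is headed as office visits and includes vital signs and spirometry, while 3.1.3 allows these control contacts by phone. Directing families to community resources could simply mean the CAPP classes. On this view the item is a stray line, not a design choice. Any dilution would push toward the null, and the figures above show that a small f is tolerable. Finally, the last dated school randomization wave was in February 2019 and the SAP was finalized in September 2022, so an edit may come too late.

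Much of this stands. The context shows which version was intended, the item is very likely a slip, and the power figures do not demonstrate a problem. P+ also includes home visits, remediation supplies, education and medication coordination, so signposting alone may carry little of its effect.

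It does not remove the conflict. No text withdraws the instruction or limits it to CAPP classes, and the CAPP reading leaves the goal-review half unexplained. The line is in the operational procedures, not in background text. The documents do not say whether follow-up had closed. If it had, reporting what controls received is still useful, because the text cannot show it.

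**Conclusion.** The concern holds: section 4.2.2 is wrong as written and contradicts sections 3.1 and 4.3.5 on a component of the intervention. That conclusion is textual and rests on no numerical assumption.

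The effect on the trial is uncertain and probably modest. It depends on whether staff followed 4.2.2 for controls and on how much of the P+ benefit comes from linkage to resources; the documents give neither. Under the illustrative assumptions, P+ v P- keeps at least 0.90 power until controls gain about 11% of the P+ effect at n=432, or about 24% at n=600. It keeps at least 0.80 until about 23% or 35%. The correction should be made because the control condition ought to be unambiguous and the change costs almost nothing, not because the trial is shown to be underpowered.

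**What to change.** - Delete the goal-review and resource item from Protocol 4.2.2 and keep it in 4.3.5.
- Add one sentence stating that control contacts at Visits 2 to 4 are for data collection only, apart from the CAPP class referral.
- Record, and report by arm, any care coordination or resource referral actually given to controls. The follow-up visit checklist named in SAP Table 6.2.3 could serve; the documents do not say whether it is completed for controls.

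The cost is one deleted line, one added sentence and, if it is not already done, completing an existing checklist for controls. No visit and no analysis model changes. If follow-up has ended, the reporting step still applies, using whatever was recorded.

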### 4.2.3 Study Visit 5 (12-Month Follow-Up)

All study participants will complete the following:

- Pulmonary function test (spirometry) with child if not obtained from medical record.
- Clinical and vital sign measurements of child [weight, height, BMI, blood pressure, pulse, temperature, pulse oximetry (SpO2)]
- 2-week parental recall of symptoms, school absences, and work days missed
- Asthma Control Questionnaire
- Caregiver's Quality of Life Questionnaire
- Cost Analysis Parent Questionnaire
- Child Asthma Risk Assessment Tool (CARAT)
- Administer Asthma Knowledge Quiz
- Observe MDI technique and complete MDI Checklist

# 4.3 Primary Care Based Intervention:

### 4.3.1 Study Visit 1 (Baseline)

Additional components of Visit 1 will include:

- Care coordination goals developed with the parent/caregiver
- Coordinate school forms, medications and devices

#### **4.3.2** Home Visit 1

Initial home visit scheduled within 2 weeks of enrollment. Primary care CHW will do the following with the child and parent/caregiver:

- Administer home environmental assessment survey
- Take photographs of child's bedroom and home's main living area (environmental remediation assessment)
- Educate about asthma basics and asthma trigger avoidance
- Review asthma medications and asthma care plan
- Administer Asthma Knowledge Quiz
- Observe MDI technique with either the child or the parent/caregiver
- Give asthma supplies tailored to environment and show caregiver how to use

- Assess possible adverse events
- Review child's medical record for utilization of healthcare services
- Establish care coordination goals and refer to community resources as needed

#### **4.3.3** Home Visit 2

Second home visit is scheduled within 4 weeks of enrollment. Primary care CHW will do the following with the child and caregiver/parent:

- Complete follow-up home environmental assessment
- Educate about types of asthma medications, how they work and how to use them properly
- Review asthma medications and asthma care plan
- Give asthma supplies tailored to environment and show caregiver how to use
- Observe MDI technique with the child or the parent/caregiver
- Assess possible adverse events
- Review child's medical record for utilization of healthcare services
- Review care coordination goals and refer to community resources as needed

### **4.3.4 Home Visit 3**

Third home visit is scheduled within 6 weeks of enrollment. Primary care CHW will do the following with the child and parent/caregiver:

- Complete follow-up home environmental assessment
- Take photographs of child's bedroom and home's main living area (environmental remediation assessment)
- Educate about communicating with teachers and family members about asthma
- Review asthma medications and asthma care plan
- Observe MDI technique with the child or the parent/caregiver
- Administer Asthma Knowledge Quiz
- Assess possible adverse events
- Review child's medical record for utilization of healthcare services

• Review care coordination goals and refer to community resources as needed

## 4.3.5 Study Visits 2, 3, and 4 (Primary Care Office Visits)

Additional components of Study Visits 2, 3, and 4 will include:

- Coordinate school forms, medications and devices
- Teach asthma care plan
- Review care coordination goals and refer to community resources as needed

# 4.3.6 Home Visit 4 (12-Month Follow-Up)

- Follow-up environmental assessment
- Take photographs of child's bedroom and home's main living area (environmental remediation assessment)
- Administer Asthma Knowledge Quiz

## In between visits:

Primary care CHW will ensure that caregiver has all forms needed for rescue
medication administration at school. Participants attending an intervention school
may have rescue and controller medications hand delivered to school nurse through
transfer from primary care CHW to school CHW at weekly meetings.

